1. BACKGROUND

1.1 PATHOPHYSIOLOGY

Diabetes is a disease of abnormal blood glucose secondary to insufficient or deficient insulin. This excess glucose is converted into alcohols through the aldose reductase pathway in tissues, the retina in particular because of the high level of aldose reductase in retinal capillaries. These alcohols result in structural changes in the capillaries that weaken them. This leads to microaneurysms, hemorrhages, increased permeability, and eventual closure of the capillaries. This results in hypoxia that causes several changes in the vasculature of the retina, including venous dilatation and new vessel growth. Areas of ischemic retina produce vasoproliferative substances, like vascular endothelial growth factor (VEGF). This stimulates the growth of new blood vessels in the retina, leading to neovascularization and proliferative diabetic retinopathy. (Aiello et al. 1999, Davis 1994)

1.2 TREATMENT OF DIABETIC NEOVASCULARIZATION

The current treatment of diabetic peripheral neovascularization is with panretinal photocoagulation. Laser photocoagulation is used to place 1200 or more 500- μ m burns, separated by one-half burn width. Treatment is divided into two or more sessions. (ETDRS Report 9. 1991)

1.3 RANIBIZUMAB AND DIABETIC NEOVASCULARIZATION

Vascular endothelial growth factor A (VEGF-A) has been implicated in the development of neovascularization in diabetes. Using ranibizumab, an anti-VEGF-A drug, would inhibit this production.

1.4 NONCLINICAL EXPERIENCE WITH RANIBIZUMAB

1.4.1 Nonclinical Pharmacokinetics

The pharmacokinetics of ranibizumab have been investigated in rabbits and cynomolgus monkeys following intravitreal and intravenous administration. In

both species, following intravitreal administration, ranibizumab was cleared from the vitreous humor with a half-life of 2–3 days. Following single intravitreal administration to cynomolgus monkeys, retinal concentrations of ranibizumab were approximately one-third of vitreous concentrations and declined in parallel with vitreous concentrations. Intravitreal injections of ranibizumab can lead to detectable antibodies in serum in rabbits and cynomolgus monkeys.

1.4.2 Nonclinical Toxicology

A series of nonclinical studies of ranibizumab administered by intravitreal injection to cynomolgus monkeys have been performed (details regarding study design and results can be found in the Investigator Brochure).

1.4.3 Stability Studies

The stability of ranibizumab alone and in combination with verteporfin was assessed in vitro. The combination of ranibizumab and verteporfin in a 5% glucose solution at concentrations of 500 µg/mL and 1.4 µg/mL, respectively, resulted in ranibizumab degradation and a decrease in ranibizumab capacity to bind VEGF. The ranibizumab degradation products have not been fully characterized. Although it is currently unknown if such degradation also occurs in vivo, sequential administration of verteporfin followed by ranibizumab with an intervening washout period will decrease the likelihood of loss of ranibizumab activity and degradation.

1.5 CLINICAL EXPERIENCE WITH RANIBIZUMAB

Ranibizumab has been or is being clinically evaluated in eight wet AMD studies (additional details regarding study design and results can be found in the Investigator Brochure).

1.5.1 Study FVF1770g

The first clinical trial with ranibizumab, Study FVF1770g was a Phase Ia study of the molecule given as a single intravitreal injection to subjects with neovascular AMD. The goals of the study were to investigate safety and tolerability and to define the maximally tolerated dose (MTD). The single intravitreal MTD was determined to be 0.5 mg (limited by ocular inflammation).

1.5.2 Study FVF2128g

The Phase I/II study FVF2128g was the first clinical trial of multiple-dose regimens of intravitreally-administered ranibizumab. Sixty-four subjects were enrolled in the study. Data show that ranibizumab was safe and potentially efficacious in subjects with subfoveal choroidal neovascularization due to AMD.

1.5.3 Study FVF2425g

Study FVF2425g was a Phase I, open-label, randomized study of three escalating multiple-dose regimens of intravitreally-administered ranibizumab. Data show that doses of ranibizumab up to 2 mg could be safely given as part of an escalating dose regimen to subjects with subfoveal choroidal neovascularization due to AMD.

1.5.4 Study FVF2428g

Study FVF2428g is an ongoing Phase I/II, single-masked, multicenter study of the safety, tolerability, and efficacy of multiple-dose intravitreal injections of ranibizumab in combination with verteporfin PDT in subjects with neovascular AMD.

Preliminary findings from Study FVF2428g suggest that administration of ranibizumab injections 7 days (± 2 days) after treatment with verteporfin PDT in the same eye may result in a decrease in visual acuity of ≥ 30 letters due to temporary intraocular inflammation (uveitis).

1.5.5 Study FVF2508g

Study FVF2508g is an ongoing Phase I extension study designed to assess the safety and tolerability of multiple-dose intravitreal injections of ranibizumab administered monthly in subjects who have completed the treatment phase of a Genentech-sponsored Phase I study.

1.5.6 Study FVF2587g

Study FVF2587g is an ongoing Phase III active treatment-controlled study designed to assess the efficacy and safety of intravitreal administered ranibizumab compared with verteporfin in subjects with angiographically determined, predominantly classic subfoveal neovascular AMD.

1.5.7 Study FVF2598g

Study FVF2598g is an ongoing Phase III study designed to assess the efficacy and safety of intravitreal injections of ranibizumab administered monthly compared with sham injections administered monthly in subjects with angiographically determined, minimally classic or occult subfoveal neovascular AMD.

1.5.8 Study FVF3192g

Study FVF3192g is an ongoing Phase IIIb study designed to assess the efficacy and safety of intravitreal injections of ranibizumab administered as three monthly injections followed by quarterly injections for a total duration of

24 months, in subjects with angiographically determined subfoveal neovascular AMD with or without classic CNV.

2. OBJECTIVES

2.1 Primary Objective

To compare the efficacy of ranibizumab versus additional panretinal photocoagulation on diabetic neovascularization that is persistent despite previous treatment with panretinal photocoagulation.

2.2 Secondary Objectives

To evaluate concomitant macular edema after intravitreal injection of ranibizumab in patients with persistent neovascularization.

3. STUDY DESIGN

3.1 DESCRIPTION OF THE STUDY

This is an open-label, Phase I/II study of intravitreally-administered ranibizumab in subjects with persistent (greater than three months) diabetic neovascularization previously treated with panretinal photocoagulation (at least 1200 or more 500- μ m burns).

Consented, enrolled subjects will either receive open-label intravitreal injections of 0.5-mg dose of ranibizumab or additional panretinal photocoagulation (up to 500 300-500 μ m laser spots) in a ratio of two-to-one (2:1) at the beginning of the study period. ETDRS best-corrected visual acuity, contrast sensitivity, and Optos color photography will be performed at enrollment, at weeks 1, 2, 3 and 4, and at months 2, 3, 4, 5 and 6. The subjects will undergo fluorescein angiography utilizing the Optomap FA (fluorescein angiography) system and optical coherence tomography (OCT) at enrollment, at weeks 2 and 4, and at months 2, 3, 4 and 6. The subjects will be followed for a 6-month period for stabilization, regression, or recurrence of

neovascularization. In addition, patients will be evaluated for occurrence of macular edema.

3.2 RATIONALE FOR STUDY DESIGN

The pathophysiology of neovascularization associated with proliferative diabetic retinopathy has been shown to be via production of VEGF-A by ischemic retinal tissue. VEGF-A is produced and can be found in the vitreous cavity where it then acts to promote neovascularization. Ranibizumab is an anti-VEGF-A drug that has been shown to bind and inhibit the action of VEGF-A. Since diabetic neovascularization is the result of VEGF-A in the vitreous cavity, intravitreal injection of ranibizumab would bind the VEGF-A produced by the ischemic retina and therefore prevent neovascularization.

3.3 OUTCOME MEASURES

- **3.3.1 Primary Outcome Measures**

The primary efficacy outcome measures include:

- The percentage change of the area of the patient's neovascularization as measured in pixels by Optomap FA
- The percentage change of macular edema measured by retinal thickness by OCT

The primary safety and tolerability outcome measures are:

- Incidence and severity of ocular adverse events, as identified by ophthalmic examination
- Incidence and severity of other adverse events, as identified by physical examination, subject reporting, and changes in vital signs

- **3.3.2 Secondary Outcome Measures**

The secondary outcome measures are:

- Mean change in Best Corrected Visual Acuity (BCVA), as assessed by the number of letters read correctly on the ETDRS eye chart at a starting test distance of 4 meters 3 and 6 months
- Percentage of patients gaining 3 or more lines of vision according to ETDRS eye chart testing
- Occurrence rate of proliferative diabetic complications including vitreous hemorrhage, iris neovascularization and tractional retinal detachment

3.4 SAFETY PLAN

The safety assessments to be conducted for this study are listed in Section 4.5 and Appendix A.

- Potential adverse events include but are not limited to local injection site reaction, subconjunctival hemorrhage, vitreous hemorrhage, retinal tear or detachment or endophthalmitis.
- If a patient has an occurrence of retinal tear or detachment or endophthalmitis:
 - The patient will not be included in the study
 - Treatment will be based on the event and at the discretion of the treating physician based on current accepted practice standards
 - Any necessary testing such as ultrasound or cultures will be performed as indicated by the specific event.
 - Any necessary procedures, such as vitreous tap and injection, laser for tears or surgical repair of detachments will be performed according to current practice standards

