4.2 METHOD OF TREATMENT ASSIGNMENT

The enrolled subjects will be randomized into two groups, 0.5 mg injection of ranibizumab or additional panretinal photocoagulation (PRP), in a two-to-one ratio (2:1). Randomization will occur by alternating treatment groups in the above ratio, as patients are included in the study. For example, Patient A and

Patient B will receive ranibizumab, Patient C will receive additional PRP, Patient D and Patient E will receive ranibizumab, etc. Therefore, seven (7) patients will receive ranibizumab and three (3) patients will receive additional PRP. There will be no masking of which treatment each patient receives.

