4.6 SUBJECT DISCONTINUATION

Subjects have a right to withdraw from the study at any time.

The subject may be withdrawn from the study for any reasons: if it is in the best interest of the subject, intercurrent illness, adverse events, or worsening

condition. Rush University Medical Center may request the withdrawal of a subject because of protocol violations, administrative reasons, or any other valid and ethical reasons.

Subjects will be discontinued and receive standard additional panretinal photocoagulation for development of neovascular glaucoma (NVG).

Other reasons for subject discontinuation may include, but are not limited to, the following:

- Sensory rhegmatogenous retinal detachment or Stage 3 or 4 macular hole
- Investigator determination that it is not in the best interest of the subject to continue participation
- Pregnancy
- Verteporfin PDT treatment in the study eye
- Pegaptanib sodium injection treatment in either eye
- SAE
- Any other safety concerns

If a subject discontinues or is discontinued from the study, he or she will not be allowed to re-enter the study.

In the event of an adverse event in the study eye that is considered by the investigator to be severe in intensity, serious consideration should be given to discontinuing the subject from the study.

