4.8 STATISTICAL METHODS

4.8.1 Analysis of the Conduct of the Study

There is no formal sample size calculation in this pilot study. As this is a phase I/II study, a sample size of 10 patients is chosen, making sure that it is feasible financially to conduct the study and logically to complete the study within 12 months. If and when the study is planned for a phase II randomized control trial, appropriate statistical analysis will be determined.

- **4.8.2 Safety Analyses**

Any adverse events, laboratory assessments, physical examinations, vital signs, ocular examinations and measurements from all 10 subjects will be utilized to summarize safety data for this pilot study.

- **4.8.3 Efficacy Analyses**

As this is a small pilot study, no formal statistical analyses are planned

- a. **Primary Endpoint**

- The percentage change of the area measured in pixels of the patient's neovascularization as measured by Optomap FA fluorescein angiography
 - The percentage change of macular edema measured by retinal thickness by OCT

- b. **Secondary Endpoints**

- Mean change in Best Corrected Visual Acuity (BCVA), as assessed by the number of letters read correctly on the ETDRS eye chart at a starting test distance of 4 meters, at 3 and 6 months

- Percentage of patients gaining 3 or more lines of vision according to ETDRS eye chart testing
- Occurrence rate of proliferative diabetic complications including vitreous hemorrhage, iris neovascularization and tractional retinal detachment

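### Section 3.4's rule for retinal tear, detachment and endophthalmitis is worded as exclusion from the study, which conflicts with the outcome definitions and with the all-subjects safety summary

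*Protocol*

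**What the plan says.** Section 3.4 of the protocol (Safety Plan) first lists potential adverse events, among them retinal tear or detachment and endophthalmitis. It then sets a rule that opens "If a patient has an occurrence of retinal tear or detachment or endophthalmitis". The first item under the rule is "The patient will not be included in the study". The remaining items describe clinical care: treatment at the physician's discretion, testing, and procedures such as vitreous tap and injection, laser and surgical repair.

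Three other places bear on the same patients:

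- Section 3.3.1 makes this a primary safety outcome: "Incidence and severity of ocular adverse events, as identified by ophthalmic examination". Section 3.3.2 lists tractional retinal detachment among the proliferative complications whose rate is a secondary outcome.
- Section 4.8.2 says that adverse events and examinations "from all 10 subjects will be utilized to summarize safety data for this pilot study".
- Section 4.6 deals with withdrawal. For neovascular glaucoma it is mandatory: "Subjects will be discontinued and receive standard additional panretinal photocoagulation for development of neovascular glaucoma (NVG"). For rhegmatogenous detachment, SAEs and other safety concerns it is permissive: "Other reasons for subject discontinuation may include, but are not limited to, the following". For a severe adverse event in the study eye, "serious consideration should be given to discontinuing the subject from the study".

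**The concern.** The sentence in 3.4 is triggered by something that happens after treatment and that the protocol itself treats as an outcome. If patients leave the study population because they had the harm being counted, the reported rate of that harm says nothing about how often it occurred. The three events are the gravest ocular events that 3.4 lists, and the arms are so small that one patient visibly changes a rate.

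Any such loss need not fall equally on the two arms. Appendix B gives endophthalmitis as an example of a risk of intravitreal injection, and only the ranibizumab arm is injected. If affected patients were removed, the omission for that event would tend to favour ranibizumab.

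This is not detail that a protocol would leave to a statistical analysis plan. It is a rule that the protocol states, and it does not fit the protocol's own outcomes and safety analysis.

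**Working it through.** **1. Arm sizes.** Section 4.2 alternates two ranibizumab patients with one photocoagulation patient. Ten patients in the order R R P R R P R R P R give 7 ranibizumab and 3 photocoagulation, the figures stated in 4.2. The safety denominator in 4.8.2 is 7 + 3 = 10.

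**2. Does the rule concern events during the study?** Yes, from its context. It follows directly on the list of potential adverse events, and its companion items describe how to treat the event. The exclusion criteria in 4.1.3 do not name these conditions.

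**3. What do the words mean elsewhere in the protocol?** Section 4.2 uses inclusion in the study for entry and allocation: "Randomization will occur by alternating treatment groups in the above ratio, as patients are included in the study". Where section 4.6 means mandatory withdrawal, it says that subjects will be discontinued. Section 3.4 uses neither discontinuation nor withdrawal. Its wording is therefore not the protocol's usual wording for stopping participation while keeping the data.

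**4. The sections side by side.**

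| Section | Effect on a patient with one of the three events |
|---|---|
| 3.4 | Not included in the study; no condition attached |
| 3.3.1 | Event belongs in the incidence of ocular adverse events |
| 3.3.2 | Event counted, if the detachment is tractional (3.4 does not restrict the type) |
| 4.8.2 | Data from all 10 subjects used |
| 5 and 5.1 | Any adverse event from Day 0 to the last study visit is collected and recorded |
| 5.5.2 | If serious, reported within 48 hours |
| 4.5.2 | On withdrawal, an early termination evaluation that covers all adverse events |

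Every row except the first points to the event being recorded, counted or followed. No section says which prevails when 3.4 and 4.8.2 disagree. The available-case rule in 4.8.4 does not settle it, because it does not say whether a patient who is not included counts as an available case.

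**5. Size if the sentence were applied as an exclusion.** The protocol gives no expected event counts, so the number of affected patients k is an assumption. In an arm of n patients, the rate with patients kept is k/n. With patients removed it is 0/(n − k), which is 0% for every k below n.

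| Group | Assumed k | Kept | Removed |
|---|---|---|---|
| Ranibizumab, n = 7 | 1 | 1/7 = 14.3% | 0/6 = 0% |
| Ranibizumab, n = 7 | 2 | 2/7 = 28.6% | 0/5 = 0% |
| Photocoagulation, n = 3 | 1 | 1/3 = 33.3% | 0/2 = 0% |
| All subjects, n = 10 | 1 | 1/10 = 10.0% | 0/9 = 0% |

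If the sentence means withdrawal with data kept, the two columns agree and the difference is zero.

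**The case against.** A reader might infer that the plan discards the data of these patients and will report 0% for the three events. The documents do not support that as the plan's intent. The sentence speaks of the patient's place in the study and stands among clinical-care instructions. It mentions no data, denominator or analysis set. To reach 0/6, someone would have to delete an event already on the case report form and override 4.8.2, the section that governs the safety analysis. This objection stands, and it is why the figures above are conditional.

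It can also be said that the wording in 4.2 suggests a bar to entry: a patient with such an event is not taken on. That reading would lose no on-study data. The list of potential adverse events before the rule and the treatment items after it weigh against it, but that a third meaning can be argued shows that the sentence is unclear.

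A reader might also infer that 3.4 and 4.6 contradict each other in a way that affects the results. They differ, since 3.4 is absolute while 4.6 is mostly permissive. But the list in 4.6 is open-ended, a stricter rule for three named events can stand beside it, and no reported rate depends on the difference. It is a mismatch of wording only.

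Finally, section 4.8.3 plans no formal efficacy statistics in this pilot, so no test or decision rule hangs on the sentence. That is true, but descriptive counts are then the main safety result, and they depend on who is counted.

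**Conclusion.** The point holds as a defect of wording with a possible consequence for the safety counts. As written, 3.4 conflicts with 4.8.2 and with the outcomes in 3.3.1 and 3.3.2. The probable intent, withdrawal with data kept, is harmless and is supported by 4.5.2, 4.8.2, 5, 5.1 and 5.5.2.

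The size is zero on the probable reading. On the less likely reading, one assumed ranibizumab event would be reported as 0/6 = 0% instead of 1/7 = 14.3%. That figure rests on the 7 and 3 arm sizes in 4.2, on an assumed event count, and on the sentence being applied as an exclusion from the summaries. The conflict between the sections rests on none of these assumptions. The sentence should be corrected because, if followed as written, it would bias the safety and complication summaries.

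**What to change.** Replace the sentence in 3.4 with:

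> *The patient may be discontinued from further study participation as in 4.6, with the early termination evaluation (4.5.2); the event and all data collected are retained, and the patient remains in all safety and complication summaries (3.3.1, 3.3.2, 4.8.2).*

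Whether discontinuation after these events should be mandatory is the investigator's clinical decision. If it should be, 3.4 and 4.6 need the same mandatory wording. The clinical-care items in 3.4 stay as they are.

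The cost is one changed sentence, plus matching words in 4.6 if discontinuation is made mandatory. No visit or procedure is added. The downside is a possibly less favourable reported adverse-event rate.

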3.5 COMPLIANCE WITH LAWS AND REGULATIONS

This study will be conducted in accordance with current U.S. Food and Drug Administration (FDA) Good Clinical Practices (GCPs), and local ethical and legal requirements.

4. MATERIALS AND METHODS

4.1 SUBJECTS

4.1.1 Subject Selection

Ten (10) subjects from one site in the United States will be enrolled. Eligible subjects will have provided informed consent. (See Appendix A, the study flow chart, for screening assessments.)

4.1.2 Inclusion Criteria

Subjects will be eligible if the following criteria are met:

- Ability to provide written informed consent and comply with study assessments for the full duration of the study
- Age \geq 18 years
- Patient-related considerations

Patients with Diabetes Mellitus (Type I or II) are eligible. HgA_{1c} will be evaluated at the beginning of the study, but this value will have no significance in inclusion or exclusion. Patients will not be pregnant at enrollment and must provide evidence of the use of two types of birth control while enrolled in the study. Patients will have no known sensitivity to ranibizumab or other anti-VEGF injections.

- Disease-related considerations

Patients will have diabetic neovascularization as seen on fluorescein angiography that was previously treated with full (at least 1200 laser burns) panretinal photocoagulation and that has persisted at least three months. There will be no evidence of ocular inflammation at enrollment. There is no restriction on patient's current medications or concomitant illnesses as long as there is no interference with patient follow-up.

- Other considerations

Patients may not be enrolled in another clinical study or observational trial. There is no limitation on patient's institutional status as long as the patient is able to participate in follow-up.

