4.1.3 Exclusion Criteria

Subjects who meet any of the following criteria will be excluded from this study:

- Pregnancy (positive pregnancy test)
- Uncontrolled glaucoma on three medicines or more to control intraocular pressure
- Prior enrollment in the study
- Any other condition that the investigator believes would pose a significant hazard to the subject if the investigational therapy were initiated
- Participation in another simultaneous medical investigation or trial

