4.4 CONCOMITANT AND EXCLUDED THERAPIES

Subjects may continue to receive all medications and standard treatments administered for their conditions at the discretion of their treating physician.

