4.8.4 Missing Data

Analyses of efficacy and safety will be based on available cases, without imputation for missing values.

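### No washout for recent anti-VEGF injection in the study eye, and no limit on non-study anti-VEGF or extra laser during follow-up (Protocol 4.1.2, 4.1.3, 4.4, 4.6)

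*Protocol*

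**What the plan says.** **Entry.** Section 4.1.2 states: "There is no restriction on patient's current medications or concomitant illnesses". The sentence is qualified only by interference with follow-up. Anti-VEGF injections appear in 4.1.2 only as a sensitivity criterion. The disease criterion asks for neovascularization on fluorescein angiography after full "panretinal photocoagulation and that has persisted at least three months". That period describes persistence of disease after laser and is not a drug washout. Section 4.1.3 has five exclusions: pregnancy, uncontrolled glaucoma on three or more medicines, prior enrollment, a condition the investigator judges hazardous, and "Participation in another simultaneous medical investigation or trial". None concerns earlier intraocular drug.

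**During follow-up.** Section 4.4 has a heading that covers excluded therapies, but its whole content is: "Subjects may continue to receive all medications and standard treatments administered for their conditions at the discretion of their treating physician". Section 4.6 makes discontinuation mandatory for neovascular glaucoma, followed by standard additional laser. It then gives an open list introduced by "Other reasons for subject discontinuation may include, but are not limited to, the following". The only therapies whose receipt is on that list are "Verteporfin PDT treatment in the study eye" and "Pegaptanib sodium injection treatment in either eye".

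**Analysis.** Section 4.8.4: "Analyses of efficacy and safety will be based on available cases, without imputation for missing values".

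**The concern.** The primary objective (2.1) compares ranibizumab with additional panretinal photocoagulation (PRP). By the protocol's own rationale (3.2), anti-VEGF in the vitreous acts on neovascularization, and change in neovascularization area is the first primary efficacy measure (3.3.1). A baseline taken while an earlier injection is still active, or a later value taken after a non-study injection or more laser, cannot be credited to the assigned treatment.

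The follow-up gap is the more important half. Ranibizumab is given once, at enrollment (4.3.2), and patients are then watched for six months for stabilization, regression or recurrence (3.1). Recurrence is when a treating physician would consider another injection or laser. Section 1.2 names PRP as the current treatment, so a broad reading of 4.4 lets a ranibizumab patient receive the comparator. On a narrow reading, which covers only therapy already under way, 4.4 is silent on new therapy. Neither reading bars it. Treatment is unmasked (4.2), so such therapy could differ by arm.

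**Working it through.** **1. Does any provision close the gap?**

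| Provision | Effect |
|---|---|
| 4.1.2, follow-up qualifier | Concerns attendance; not a washout |
| 4.1.2, three-month persistence | Partial filter: a fully regressed eye fails it, a partly responding eye can pass. It does not act on OCT, because no entry criterion refers to retinal thickness |
| 4.1.3, hazard exclusion | A safety test; does not protect the baseline |
| 4.6, protocol violations | Because 4.4 bars nothing, non-study ocular therapy is not a violation |
| 4.6, PDT and pegaptanib | Discretionary, and limited to those two |

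None closes it.

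**2. Weight of one patient.** The 2:1 alternation in 4.2 (two ranibizumab, one PRP, repeated) gives 7 and 3 for ten patients, as stated there. One patient is 1/7 = 14.3% or 1/3 = 33.3% of an arm. If non-study therapy moves one patient's percentage change by E points, the arm mean moves by E/n. The values of E are assumptions, as the documents give none:

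| E | PRP mean, E/3 | Ranibizumab mean, E/7 |
|---|---|---|
| 20 | 6.7 | 2.9 |
| 50 | 16.7 | 7.1 |
| 80 | 26.7 | 11.4 |

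**3. How likely is at least one?** The frequency is not in the documents. With an assumed proportion p of affected patients, independent of one another, the chance of at least one among n is 1 − (1 − p)^n:

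| p | Among 10 | Among the 3 PRP patients |
|---|---|---|
| 5% | 40% | 14% |
| 10% | 65% | 27% |
| 20% | 89% | 49% |
| 30% | 97% | 66% |

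**4. How long does earlier ranibizumab remain?** Section 1.4.1 gives a vitreous half-life h of 2–3 days in animals. Five half-lives are 5 × 2 = 10 to 5 × 3 = 15 days. If the human half-life is twice as long (assumption, 4–6 days), they are 20 to 30 days. The fraction left at day t is 2^(−t/h):

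| Day | h = 2 | h = 3 | h = 4 | h = 6 |
|---|---|---|---|---|
| 7 | 8.8% | 19.8% | 29.7% | 44.5% |
| 14 | 0.8% | 3.9% | 8.8% | 19.8% |
| 15 | 0.6% | 3.1% | 7.4% | 17.7% |
| 30 | <0.1% | 0.1% | 0.6% | 3.1% |

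For ranibizumab, residual drug at baseline is therefore a matter of roughly the last two to four weeks before enrollment. This is drug present, not duration of effect. Other agents cannot be computed from the documents.

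**5. Exposure on study.** Sections 3.1 and 4.5.1 place angiography and OCT at weeks 2 and 4 and months 2, 3, 4 and 6. Five of these six visits fall after day 15 and four after day 30 (week 4 is day 28). At those visits little of the single study dose remains, and a non-study injection would be the main anti-VEGF exposure.

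**The case against.** The strongest defense is that this is a ten-patient, single-site, unmasked pilot with allocation by open alternation and no formal analysis (4.2, 4.8). Broad eligibility is deliberate and helps feasibility. The protocol describes ranibizumab as evaluated in wet AMD studies (1.5) and bars simultaneous trials, so earlier ranibizumab in a diabetic eye looks remote. Medical history is taken at enrollment, section 4.6 allows withdrawal for any valid and ethical reason, and the handling of values after non-study therapy is commonly left to a statistical analysis plan, which was not available.

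Much of this stands. The half-life figures cover prior ranibizumab only, and the frequency is unknown. The absence of a reporting rule is not itself a fault of the protocol.

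Three things remain. Eligibility and permitted therapy are protocol matters, and here they are fixed as unrestricted; no analysis plan can restore a contaminated baseline. Taking a history does not exclude anyone, and discretionary withdrawal in unmasked care can itself differ by arm. The remoteness of prior ranibizumab also does not answer the on-study gap, since standard treatment is expressly permitted and PRP is the standard.

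A reader might go further in three ways that the documents do not support:

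- **Steroid.** One might infer that intraocular steroid is an equal threat. Nothing in the protocol says that steroid acts on either measure.
- **OCT thickness.** One might infer that it is certainly biased. Section 2.2 only sets out to evaluate edema after injection and states no direction of effect, and the mechanism in 3.2 concerns neovascularization.
- **Section 4.6.** One might infer that it mentions no treatment beyond PDT and pegaptanib. It also mentions PRP, as care after discontinuation for neovascular glaucoma.

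**Conclusion.** The concern holds for intravitreal anti-VEGF before and during the study, and for laser beyond the assigned treatment during the study, in the study eye. The protocol's permissive rule can confound its own primary comparison of neovascularization area, and possibly of OCT thickness. With no test planned, the harm is to the attribution of descriptive results, not to an error rate or power.

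The fixed part of the size is arm weight: 14% or 33% per affected patient. The mean shifts, the chance of at least one case and the doubled half-life rest on assumed values and show scale only. A reader might infer that baselines will be contaminated or that the comparison is already invalid. The documents do not show this, because they give no frequency and the persistence criterion filters some cases. Severity is minor to moderate, and the change is worth making because it is cheap.

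**What to change.** 1. **Section 4.1.3:** exclude study eyes given intravitreal anti-VEGF within a stated washout. For ranibizumab, 15 days follows from the animal half-life, and 30 days also covers a doubled half-life (assumption). The sponsor should set the period for other agents. Intraocular steroid may be added on the sponsor's clinical judgment, but the documents supply no basis for it.
2. **Section 4.4:** state that non-study anti-VEGF and laser beyond the assigned treatment are not permitted in the study eye during follow-up unless clinically necessary. If given, record the date and reason.
3. **After such therapy:** continue scheduled visits unless 4.6 applies, and identify or separate the later measurements when reporting. The neovascular glaucoma rule stays mandatory and takes precedence. PDT and pegaptanib stay as discretionary discontinuation reasons. Other therapies should not be added to that list, because a withdrawn subject has only one early-termination evaluation (4.5.2) and missing values are not imputed.

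**Cost:** a short amendment and one case report form line, plus a delay in entry for recently injected eyes only, whose number is unknown. If the 12 months in 4.8.1 include the six months of follow-up, about six months (182.5 days) remain for enrollment. A 15-day wait uses 15/182.5 = 8.2% of that window for an affected patient, and a 30-day wait 30/182.5 = 16.4%.
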